## Clinical Investigation Plan

6. Myocardial infarction (MI), acute coronary syndrome, percutaneous coronary intervention (PCI), or valve or coronary bypass grafting surgery within 90 days of procedure
7. Left atrial diameter > 5.0 cm measured within 180 days of procedure (echocardiography or CT)
8. Left ventricular ejection fraction < 35% measured within 180 days of procedure (echocardiography or CT)
9. New York Heart Association (NYHA) class III or IV
10. Previous left atrial surgical or catheter ablation procedure
11. Left atrial surgical procedure or incision with resulting scar (including LAA closure device)
12. Previous tricuspid or mitral valve replacement or repair
13. Heart disease in which corrective surgery is anticipated within 180 days after the procedure
14. Bleeding diathesis or suspected pro-coagulant state
15. Contraindication to long term anti-thromboembolic therapy
16. Presence of any condition that precludes appropriate vascular access
17. Renal failure requiring dialysis
18. Known sensitivity to contrast media (if needed during the procedure) that cannot be controlled with pre-medication
19. Severe pulmonary disease (e.g., restrictive pulmonary disease, constrictive or chronic obstructive pulmonary disease) or any other disease or malfunction of the lungs or respiratory system that produces severe chronic symptoms
20. Women who are pregnant or breastfeeding
21. Presence of other anatomic or comorbid condition that, in the investigator's opinion, could limit the patient's ability to participate in the clinical trial or to comply with follow up requirements, or impact the scientific soundness of the clinical trial results
22. Patient is currently participating in another clinical trial or has participated in a clinical trial within 30 days prior to screening that may interfere with this clinical trial
23. Patient is unlikely to survive the protocol follow up period of 12-months after the procedure
24. Body mass index > 40 kg/m^2
25. Presence of other medical, social, or psychological conditions that, in the investigator's opinion, could limit the subject's ability to participate in the clinical investigation or to comply with follow-up requirements, or impact the scientific soundness of the clinical investigation results.
26. Individuals without legal authority
27. Individuals unable to read or write
28. Patients who have had a ventriculotomy or atriotomy within the preceding 4 weeks of procedure,
29. Patients with prosthetic valves,
30. Patients with a myxoma,
31. Patients with an interatrial baffle or patch as the transseptal puncture could persist and produce an iatrogenic atrial shunt
32. Patient unable to receive heparin or an acceptable alternative to achieve adequate anticoagulation
33. Stroke or TIA (transient ischemic attack) within the last 90 days
34. Stent, constriction, or stenosis in a pulmonary vein.
35. Rheumatic heart disease
36. Severe mitral regurgitation (regurgitant volume  $\geq$  60 mL/beat, regurgitant fraction  $\geq$  50%, and/or effective regurgitant orifice area  $\geq$  0.40cm^2).

## Clinical Investigation Plan

### APPENDIX XI: GERMAN HANDLING OF SERIOUS ADVERSE EVENTS

The scope of this section is to implement the reporting obligation in accordance with §3, section 5 of the German MPSV (Medical Products Safety Ordinance), taking into consideration that notification must be done immediately in accordance § 5, section 2 of the MPSV.

1. Definition of SAE according to §2, Section 5 MPSV:  
Serious Adverse Event: any untoward event occurring within a clinical investigation requiring authorization, which directly or indirectly led to, or which might have led or could lead to death or a serious deterioration in the health of the patient, a user or other person, without taking into account whether the event was caused by the medical device.
  
2. Notification of SAEs:
  - As soon as the investigator becomes aware of an SAE during the course of a study, the sponsor (Abbott) must be informed immediately, and in no case later than 72 hours after becoming aware.
  - The sponsor (Abbott) also has the obligation to inform the BfArM of all SAEs according to following table.

Condition for reporting to BfArM	Country of occurrence	Timeline for reporting to BfArM	Form
a causal relationship between the SAE and the investigational medical device, a comparator device, diagnostic or therapeutic procedures performed as part of the clinical trial or other conditions of the trial conduct cannot be excluded	Germany	immediately	German SAE Report Form (latest version) for single reports
	all other countries where the clinical trial is performed	immediately	MEDDEV 2.7/3 Report Table Please document all SAEs cumulatively on the same spreadsheet Report to be sent to [contact]
a causal relationship between the SAE and the investigational medical device, a comparator device, diagnostic or therapeutic procedures performed as part of the clinical trial or other conditions of the trial conduct can be excluded	Germany	quarterly	
 
• Quarterly Report Template V1.0
 
• Table Complication Rates
 
• MEDDEV 2.7/3 Report Table
 
 Please document all SAEs cumulatively on the same spreadsheet Report to be sent to [contact]
	all other countries where the clinical trial is performed	quarterly	

## Clinical Investigation Plan

- The German [SAE Report Form](http://www.bfarm.de/DE/Medizinprodukte/form/functions/formmp-node.html) is available on the BfArM homepage: <http://www.bfarm.de/DE/Medizinprodukte/form/functions/formmp-node.html>
  - Please note that the SAE gets a unique ID which consists of 4 Parts:
    - The Study Code [REDACTED]
    - The Center ID (ORACLEID = Center Name)
    - The Patient No
    - The Date of SAE in the format (Year (2-digits) Month Day)  
(Example: CRD\_858\_EU0284\_01\_160203 for an event which occurred on 3 February for Patient 1 in center EU0284 within the Study CRD\_858).
  - The German Quarterly Report Template is available on the BfArM Homepage: [http://www.bfarm.de/SharedDocs/Formulare/DE/Medizinprodukte/SAE\\_Berichtsvorlage.docx](http://www.bfarm.de/SharedDocs/Formulare/DE/Medizinprodukte/SAE_Berichtsvorlage.docx)  
Table Complication Rates  
[http://www.bfarm.de/SharedDocs/Formulare/DE/Medizinprodukte/SAE\\_Komplikationsrate.xls](http://www.bfarm.de/SharedDocs/Formulare/DE/Medizinprodukte/SAE_Komplikationsrate.xls)  
[X](#)  
Instructions for completing the quarterly assessment form for serious adverse events  
[http://www.bfarm.de/SharedDocs/Formulare/DE/Medizinprodukte/SAE\\_Berichtsvorlage\\_Hinweisblatt.pdf](http://www.bfarm.de/SharedDocs/Formulare/DE/Medizinprodukte/SAE_Berichtsvorlage_Hinweisblatt.pdf)
  - The investigator will be instructed on this obligation during the initiation visit.
  - Information about the obligation must be documented in the "training log".
  - Written confirmation that this working procedure has been passed on to the trial center is sent to the investigator and then attached to the study file.
3. Responsibility of the investigators:
- The investigator has to notify the SAE to the sponsor without undue delay.
  - SAEs should be reported either by
    - i. EDC (primary reporting tool)
    - ii. E-Mail: [REDACTED]
  - The investigator or main investigator is obliged to respect the deadline for notification of SAEs.
  - A person within the study center will be designated to collect the necessary information.
  - A person within the study center will be designated to pass on this information to the sponsor. A list of people (including a representative) will be prepared for this purpose.
4. Responsibilities of the monitor (Abbott):
- The monitor will be instructed of his/her responsibilities with regard to SAEs.
  - If the monitor discovers an SAE during the course of the study that was not notified or not notified within the notification deadline, the sponsor's action plan will take effect. The BfArM is then notified of the SAE without undue delay and the investigator is informed of it straight away.
5. Responsibilities of the Sponsor
- The Sponsor (Abbott) shall notify any SAEs without undue delay (at the latest however within 3 calendar days) after awareness.
  - A person will be designated to verify SAEs that occur during the clinical study.
  - A list of Abbott people who shall be informed about SAEs is to be drawn up.
  - A person will be designated who is responsible for the assessment of any SAEs.

## Clinical Investigation Plan

- A person or team will be designated who is responsible for initiating corrective actions if necessary.
6. Responsibilities of the sponsor in Germany
- All people within Abbott Medical GmbH who are involved in this clinical study be will instructed of the notification deadlines and are obliged to respect them.
  - SAEs/PERs (Product Event Reports) are coordinated by Clinical Safety or by [REDACTED] (Manager Field Clinical Submission Specialists, Germany).
  - SAE notifications to the BfArM are to be made by Clinical Safety.
  - Vigilanz-Responsible for this study: [REDACTED] (Manager Field Clinical Submission Specialists, Abbott Medical GmbH, Germany)  
Phone: [REDACTED]
7. Notification of SAEs in other countries
- A list of the EU countries or other geographies with potential study sites outside of Germany are listed below. SAEs will also be reported in the EU countries or other geographies that have sites participating in this clinical investigation.
    - Australia
    - Austria
    - Canada
    - Czech Republic
    - Denmark
    - France
    - Holland
    - Hong Kong
    - Italy
    - Poland
    - Serbia
    - Spain
    - Taipei
    - United Kingdom
    - United States

1.0 SYNOPSIS OF STUDY DESIGN

1.1 Purpose of the Statistical Analysis Plan

This statistical analysis plan (SAP) is intended to provide a detailed and comprehensive description of the planned methodology and analysis to be used for [REDACTED], the [REDACTED] TactiFlex PAF IDE clinical investigation. [REDACTED]

1.2 Clinical Investigation Objectives

1.2.1 Primary Objective

The primary objective of the TactiFlex PAF IDE clinical trial is to demonstrate that ablation with the TactiFlex Ablation Catheter, Sensor-Enabled™ (TactiFlex SE), in conjunction with a compatible RF generator and three-dimensional mapping system, is safe and effective for the treatment of drug refractory, symptomatic paroxysmal atrial fibrillation (PAF) when following standard electrophysiology mapping and radiofrequency (RF) ablation procedures.

1.2.2 Secondary Objectives

The TactiFlex PAF IDE clinical trial has two secondary objectives:

1. To provide supporting data for the safety and effectiveness of using TactiFlex SE at 40-50 Watts in the left atrium as part of an AF ablation procedure.
2. To provide supporting data for the safety and effectiveness of using TactiFlex SE to treat cavo-tricuspid isthmus (CTI)-dependent (or “typical”) atrial flutter (AFL) through the ablation of the CTI in the right atrium. This data may be used to support an expanded indication for the treatment of CTI-dependent AFL.

1.3 Clinical Investigation Design

This is a prospective, non-randomized, multi-center pivotal clinical trial to evaluate the safety and effectiveness of ablation with the TactiFlex SE catheter for the treatment of PAF compared to pre-determined performance goals. The study design includes a substudy to assure that there will be at least 50 subjects ablated at the high-end of the ablation power setting recommendations in the investigational *Instructions for Use* document. Subjects in the HSP (High Standard Power) substudy are to undergo the same study procedures as subjects in the main study, except that ablation power settings of 40-50 Watts are to be used in the left atrium, unless there is a medical reason to use a lower power. Operators will be assigned to either the main study or the HSP substudy based on the ablation power settings they currently use in their standard practice. Subjects will be enrolled in either the main study or the substudy at the point of consent based on the operator that is expected to perform their ablation procedure. After the substudy has enrolled 50 subjects, or if the Sponsor has provided written permission, HSP operators may transition to the main study and treat main study subjects. No site may enroll more than 10 subjects (20%) in the HSP substudy without Sponsor pre-approval and at least 25 HSP substudy subjects (50%) must be from the United States.

Up to 40 sites worldwide will participate in the TactiFlex PAF IDE clinical study. The TactiFlex IDE Clinical Study will enroll a total of 355 subjects. Fifty (50) subjects will be enrolled in the HSP Substudy and 305 subjects will be enrolled in the Main Study. No center may contribute more than 20% (N=61) of

Statistical Analysis Plan

the total number of enrollments in the main study without Sponsor pre-approval. At least 50% (N=153) of the subjects will be from the US.

[REDACTED] Subjects will be followed for 12-months after their initial ablation procedure. The primary and secondary endpoints will be evaluated when all subjects have completed their 12-month follow-up visit. [REDACTED]

[REDACTED] All adverse events (AEs), with logical exceptions, from the point of enrollment through study exit will be documented and reported. A Clinical Event Committee (CEC) will be used to adjudicate all AEs that are determined by the Sponsor to potentially meet the criteria of 1) a serious AE and/or 2) an AE related to the investigational devices or ablation procedure.

The clinical investigation has been designed to involve as little pain, discomfort, fear, and any other foreseeable risk as possible for subjects. Refer to the Risks Analysis section of the clinical investigation plan for details.

1.4 Endpoints

1.4.1 Primary Endpoints

1.4.1.1 Primary Safety Endpoint

The primary safety endpoint is the rate of device and/or procedure-related serious adverse events with onset within 7-days of any ablation procedure that uses the TactiFlex SE catheter (initial or repeat procedure performed 31-80 days of initial procedure) that are defined below:

- Atrio-esophageal fistula¹
- Cardiac tamponade/perforation¹
- Death
- Heart block
- Myocardial infarction
- Pericarditis
- Phrenic nerve injury resulting in diaphragmatic paralysis
- Pulmonary edema
- Pulmonary vein stenosis¹
- Stroke/cerebrovascular accident
- Thromboembolism
- Transient ischemic attack
- Vagal nerve injury/gastroparesis
- Vascular access complications (including major bleeding events²)

1. Atrio-esophageal fistula, cardiac tamponade/perforation and pulmonary vein stenosis will be evaluated through 12-months.

2. Bleeding is a major complication of AF ablation if it requires and/or is treated with transfusion or results in a 20% or greater fall in hematocrit.

These events must meet the criteria listed in **Appendix A** to be included in the primary endpoint as adjudicated by the clinical events committee (CEC).

The performance goal is set at [REDACTED] as determined by relevant studies for PAF that utilize radiofrequency ablation.

Statistical Analysis Plan

1.4.1.2 Primary Effectiveness Endpoint

The primary effectiveness endpoint for this clinical trial is freedom from documented (symptomatic or asymptomatic) AF/AFL/AT episodes of >30 seconds duration that are documented by 12-lead ECG, transtelephonic monitoring (TTM) or Holter monitor after the initial catheter ablation procedure through 12-months of follow-up (9 months after a 90-day blanking period).

AF/AFL/AT recurrence during the 90-day blanking period (≤ 90 days post-initial procedure) will not be considered a treatment failure. One repeat procedure will be allowed for ablation of AF/AFL/AT recurrence 31-80 days after the initial procedure and will not be considered a treatment failure. Failure to achieve acute procedural success (confirmation of entrance block after a 20-minute minimum waiting period) during the last ablation procedure¹ with the TactiFlex SE catheter will constitute failure to achieve this endpoint. After the 90-day blanking period, use of Class I or III AADs will not count as a therapy failure provided that only previously failed Class I or III AADs are taken at doses that do not exceed the previously failed dose.

AF/AFL/AT recurrence will only be assessed by 12-lead ECG, TTM, and Holter monitoring devices for assessment of this primary endpoint so that all subjects are monitored equally with devices of the same sensitivity and specificity (recurrence data collected from other devices such as pacemakers, ICDs, or ICMs will not be included in the assessment). ECG, TTM, and Holter data collected from sites will be evaluated by a core laboratory to ensure independent and unbiased assessment of AF/AFL/AT recurrence for endpoint analysis.

There are multiple situations in which subjects will be considered primary effectiveness endpoint failures:

- If the subject fails to achieve acute procedural success, defined as confirmation of entrance block in all pulmonary veins after a minimum waiting period of 20-minutes, during last ablation procedure performed with the TactiFlex SE catheter, or
- If documented AF/AFL/AT recurrence (>30 second episode) occurs at any time after the blanking period (>90 days after the initial procedure), or
- If the subject requires a repeat procedure for the treatment of AF >80 days after the initial procedure, the subject will be considered an effectiveness endpoint failure regardless of documentation of a >30 second AF/AFL/AT episode, or
- If the subject requires a second repeat AF ablation procedure ≤ 80 days after the initial procedure, or
- Any use of a new class I or III AAD for AF after the blanking period, or
- Any use of a class I or III ADD for AF at a dose higher than that previously failed by the patient, or
- If the subject requires a cardioversion (electrical or pharmacological) for the treatment of AF after the blanking period, or
- If the subject has a continuous atrial arrhythmia throughout a 12-lead ECG recording after the blanking period indicating AF/AFL/AT recurrence, this will be considered sufficient documentation of recurrence unless there is evidence that the recorded arrhythmia is short-lived and less than 30 seconds as determined by the investigator, or
- Any ablation in the left atrium using an ablation catheter other than TactiFlex SE.

¹ For subjects that have a repeat ablation procedure ≤ 80 days after the initial procedure, only failure to achieve acute procedural success during the repeat procedure will contribute to primary effectiveness endpoint.

Statistical Analysis Plan

Cavotricuspid isthmus (CTI)-dependent AFL that occurs alone either during or after the blanking period will be considered an exception to being considered a recurrence, as CTI-dependent AFL is easily treated with cavotricuspid isthmus ablation and is not an iatrogenic arrhythmia following a left atrial ablation procedure for AF. Occurrence of CTI-dependent AFL confirmed by entrainment maneuvers that occurs at any time during the follow-up period and is ablated, will not be considered a primary effectiveness endpoint failure.

Counting the use of new or higher than previously failed doses of AADs after the blanking period as effectiveness failures is consistent with the primary effectiveness endpoint recommendations in the FDA Guidance on Clinical Study Designs for Percutaneous Catheter Ablation for the Treatment of Atrial Fibrillation [14].

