## Clinical Investigation Plan

right to withdraw at any time without penalty or loss of benefit. Conceivable reasons for discontinuation may include, but not be limited to, the following:

- Subject death
- Subject voluntary withdrawal
- Subject lost-to follow-up as described below
- Subject fails to meet all Eligibility Criteria (**Section 5.3**)
- Procedure is aborted prior to (ablation) catheter insertion
- Procedure is aborted prior to RF energy delivery
- Subject's follow-up is terminated according to **Sections 6.6.1-6.6.2**.

The Sponsor must be notified of the reason(s) for subject discontinuation. The site will provide this information to the Sponsor. Investigators must also report this to their respective IRB/EC as defined by their institution's procedure(s).

No additional follow-up will be required or data recorded from subjects once withdrawn from the clinical investigation, except for the status (deceased/alive).

In case of subject withdrawal of consent, the site should make attempts to schedule the subject for a final clinical investigation visit. At this final follow-up visit, the subject will undergo the assessments as outlined for an unscheduled visit in **Section 6.6.5** if the visit does not coincide with a scheduled follow-up visit.

Withdrawn subjects count towards the total enrollment at the site and will not be replaced by enrolling additional subjects.

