2.2.3 Survival Analyses

Survival analysis will be conducted to analyze time-to-event variables. Subjects without events will be censored at their last known event-free time point. Survival curves will be constructed using Kaplan-Meier estimates.

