2.3 Endpoint Analysis

2.3.1 Primary Endpoints

2.3.1.1 Primary Safety Endpoint

The primary safety endpoint is the rate of device and/or procedure-related serious adverse events with onset within 7-days of any ablation procedure that uses the TactiFlex SE catheter (initial or repeat procedure performed 31-80 days of initial procedure).

The primary safety endpoint hypothesis is stated as follows:

$$H_0: P_S \geq [REDACTED]$$

$$H_a: P_S < [REDACTED]$$

where P_S is the percentage of subjects with a primary safety endpoint event and [REDACTED] is the performance goal. [REDACTED]

Events will be adjudicated by the Clinical Events Committee (CEC).

Statistical Analysis Plan

[REDACTED]

[REDACTED]

[REDACTED]

The primary effectiveness endpoint rate will be calculated using the Kaplan-Meier method based on the primary effectiveness analysis population. [REDACTED]

[REDACTED]

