3.3 Subject Early Termination

Subject early termination reasons including deaths, withdrawals, and lost-to-follow-up and will be summarized from the time the subject signs consent until they exit the study.

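### Death is absent from the effectiveness failure list, and under the only readable censoring rule a related death after confirmed isolation is credited with the survivors' success rate

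*SAP*

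**What the plan says.** The endpoint in SAP 1.4.1.2 is worded as an arrhythmia outcome: "The primary effectiveness endpoint for this clinical trial is freedom from documented (symptomatic or asymptomatic) AF/AFL/AT episodes of >30 seconds duration". A list of failures follows, introduced by "There are multiple situations in which subjects will be considered primary effectiveness endpoint failures". It has nine items, from acute procedural failure ("If the subject fails to achieve acute procedural success, defined as confirmation of entrance block in all pulmonary veins") to "Any ablation in the left atrium using an ablation catheter other than TactiFlex SE". CIP 4.1.2 carries the same nine. Death is not among them, and nothing inside either list is blacked out.

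On estimation, the readable part of SAP 2.3.1 says: "The primary effectiveness endpoint rate will be calculated using the Kaplan-Meier method based on the primary effectiveness analysis population". The general rule in SAP 2.2.3 is: "Subjects without events will be censored at their last known event-free time point". No readable sentence makes an exception for death.

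Death is otherwise handled as a form of exit. In CIP 5.5 it heads the list introduced by "Conceivable reasons for discontinuation may include, but not be limited to, the following", and SAP 3.3 will summarise "Subject early termination reasons including deaths, withdrawals, and lost-to-follow-up".

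**The concern.** Recurrence in the first 90 days cannot count as failure. A subject with confirmed entrance block who dies of a complication in that window therefore meets none of the nine items and, on the readable rule, leaves the risk set as a censored non-failure. Kaplan-Meier then treats that subject as if the chance of success were the same as for those who remained under observation. That needs non-informative censoring, which is hard to defend when the treatment under test caused the exit.

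The direction is fixed: censoring a death instead of failing it can only raise the estimate tested against the 50% goal. The AAD-free, single-procedure and symptomatic secondary endpoints take their definition from the primary and inherit the gap.

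**Working it through.** The plan states no figure on this point to reproduce. The sample-size sections are redacted, so alpha, power, expected success and attrition cannot be read.

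**Inputs.** From the documents: main-study N = 305 (CIP 5.6), effectiveness goal 50% (CIP 4.1.2), safety goal 12.9% (CIP 4.1.1). Assumed: success S of 55-70%, one-sided alpha 0.025 (lower limit = estimate minus 1.96 SE), no other censoring, and 0 to 2 related deaths.

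**Mechanism.** Let d subjects die before any failure can accrue, and let x of the other 305 − d succeed.
- Deaths censored: estimate = x/(305 − d), exactly the survivors' success rate.
- Deaths as failures: estimate = x/305.
- Difference = (d/305) × x/(305 − d), that is (d/305) × S.

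Check with d = 3 and x = 181: 181/302 = 59.93% against 181/305 = 59.34%, a difference of 0.59 points.

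**Size.**
- One early death: 0.55/305 = 0.18 points to 0.70/305 = 0.23 points.
- Two early deaths: 2 × 0.55/305 = 0.36 points to 2 × 0.70/305 = 0.46 points.

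These figures are for deaths in the blanking period. A subject who dies event-free later is credited with the higher success rate of those still at risk, so the shift per such death rises towards its ceiling of 1/305 = 0.33 points.

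**Effect on the test against 50%.** Without other censoring, SE = √(p(1 − p)/n).

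| Early deaths | Successes | Censored: estimate (lower limit) | Failure: estimate (lower limit) |
|---|---|---|---|
| 3 | 181 | 59.9% (54.4%) | 59.3% (53.8%) |
| 2 | 170 | 56.1% (50.5%) | 55.7% (50.2%) |
| 2 | 169 | 55.8% (50.2%) | 55.4% (49.8%) |
| 3 | 169 | 56.0% (50.4%) | 55.4% (49.8%) |

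On these assumptions the scoring of deaths decides the result only at about 56% success. With two deaths it does so at 169 successes but not at 170. At 60% or more it changes nothing.

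**The case against.** There are four serious objections.

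**Redaction.** Text beside the Kaplan-Meier sentence, the effectiveness population (SAP 2.1.4) and the multiple-imputation, best-case and worst-case analyses (SAP 2.13.1 to 2.13.3) are blacked out. The SAP's references include a multiple-imputation method for survival data in which censoring may be informative. A rule for deaths may sit in any of these places. This stands. A reader might infer that the plan definitely censors procedure-related deaths, but the documents show only that the readable rule would. The absence of death from the failure list is not an inference.

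**Some deaths already fail.** A death before entrance block is confirmed arguably fails under the first item, and a subject with a qualifying failure before death is already counted. This also stands. The documents do not support the reading that every subject killed by the ablation is credited with success. The gap is death after confirmed isolation with no prior failure.

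**Harm belongs to the other co-primary.** Related death with onset within 7 days is a safety event, fistula, tamponade/perforation and pulmonary vein stenosis are evaluated through 12 months, and CIP 8.11 requires both nulls to be rejected. This reduces the concern but does not remove it. A fatal related event of another type with onset after day 7, such as a stroke, would count in neither co-primary. Safety events are also pooled: an exact test of 12.9% at the assumed alpha with 305 subjects tolerates 27 events (8.9%), so two deaths would not decide it. Neither fact alters the effectiveness rate.

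**It is an arrhythmia endpoint by design.** Keeping arrhythmia freedom and harm apart is a legitimate choice. But the list already counts treatment failures without documented arrhythmia, such as missing entrance block or using another left atrial catheter, so the design argument does not fully explain leaving out a death caused by the ablation.

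**Conclusion.** The concern holds in limited form. The omission from the failure list is certain; censoring follows from the only readable rule and is subject to redacted text. The bias always favours the device and is about (deaths/305) × success rate: at most about 0.5 points for an assumed 0 to 2 related deaths in the blanking period. It could affect the conclusion only if the result lands close to the 50% goal.

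Two larger readings should be resisted. Applying the 3% annual death rate in CIP 1.1.1 gives 305 × 0.03, about 9 deaths, and 9 × 0.55/305 to 9 × 0.70/305, or 1.6 to 2.1 points. That rate is all-cause and comes from trials in anticoagulated AF patients, whereas this trial excludes patients unlikely to survive 12 months. It can serve as an upper figure for an any-death sensitivity analysis but not for related deaths. Nor can it be said that the secondary endpoints are more exposed because their goals are tighter, since those goals are redacted.

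**What to change.** Unless a redacted rule already does so:

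1. Add one item to the failure lists in SAP 1.4.1.2 and CIP 4.1.2: *death adjudicated by the CEC as device- or procedure-related before the 12-month assessment*, with failure dated at death. The three secondary endpoints inherit it.
2. Report one sensitivity analysis that counts any death before 12 months as a failure, or confirm that the Worst Case analysis in SAP 2.13.3 already does this.

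If a redacted section already settles the matter, it is enough to bring the endpoint text into line with it.

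The cost is one list item and one extra run. CIP 10.9.4 already has the CEC adjudicate serious and related events, so no new data are needed. The downside is that the stated success rate may fall by a few tenths of a point.
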